**Part 1B Macro Seed for Parameter Estimation Using Bayesian MCMC Procedure**

Endpoint	Input Dataset	Macro Seed
Percentage of Rescue Free Days	Observed Dataset A	9170
	Observed Dataset B	5337

**Part 2B Macro Seeds for Multiple Imputation of Datasets**

Endpoint	Multiple Imputation Method	Macro Seed	Output Dataset
Percentage of Rescue Free Days	MAR	2553	MAR Dataset A
	J2R	8350	J2R Dataset A
	MAR	4380	MAR Dataset B
	J2R	2045	J2R Dataset B

### 10.5.3.3. Patient Reported Outcomes

Asthma Control Test (ACT)					
The ACT is a validated self-administered questionnaire utilising 5 questions to assess asthma control during the past 4 weeks on a 5-point categorical scale (1 to 5).					
By answering all 5 questions, a participant with asthma can obtain a score that may range between 5 and 25, with higher scores indicating better control. An ACT total score of 5 to 19 suggests that the participant's asthma is unlikely to be well controlled. A score of 20 to 25 suggests that the participant's asthma is likely to be well controlled. The minimally important difference (MID) for ACT is 3 [Schatz, 2009].					
The total score is calculated as the sum of the scores from all 5 questions [Nathan, 2004], provided all scores are non-missing; if any individual scores are missing then the overall score will be set to missing. The ACT total scores calculated using the electronic version on the ePRO device will be used; i.e. total scores will not be rederived from the individual question responses.					
ACT will be completed on an ePRO device at the clinical study site and at the times detailed in Appendix 1: Schedule of Activities .					
Asthma Symptom Utility Index (ASUI)					
The ASUI is a 10-item self-administered questionnaire with 4 questions on asthma symptoms (Cough, wheeze, shortness of breath, awakening at night) and 1 question about the side effects of asthma medications [Revicki, 1998].					
For each symptom, there are 2 dimensions; frequency and severity. The questionnaire is based on a 2-week patient recall of symptoms with response options of 0 to 4 for frequency (not at all, 1 to 3 days, 4 to 7 days, and 8 to 14 days) and severity (not applicable, mild, moderate and severe).					
ASUI score ranges from 0 (worst possible symptoms) to 1 (no symptoms) and the MID of the ASUI is considered to be 0.09 [Bime, 2012]. If the response to any question is missing then the ASUI is also set to missing.					
A multi-attributable utility theory was used to construct a model for calculating ASUI utilities from individual patient responses [Revicki, 1998]. The multi-attributable utility function is:					
ASUI = 1.200 × (s1 × s2 × s3 × s4 × s5) - 0.200					
where ASUI is the utility of the symptom state on a scale where the best state (no symptoms) has a score of 1 and worst possible symptoms (severe symptoms for 8 to 14 days) has a score of 0; and s i is the score for the level on symptom i. The table below shows the coefficients for calculating the ASUI scores:					
Symptom (Attribute)					
Level, d	Cough, S 1	Wheeze, S 2	Dyspnoea, S 3	Awaken at Night, S 4	Medication Side Effects, S 5
1 None	1.0	1.0	1.0	1.0	1.0
2 Mild, 1-3	0.985	0.962	0.946	0.955	0.970
3 Mild, 4-7	0.963	0.940	0.920	0.931	0.954
4 Mild, 8-14	0.935	0.913	0.885	0.899	0.930
5 Moderate, 1-3	0.955	0.913	0.892	0.909	0.924
6 Moderate, 4-7	0.920	0.886	0.860	0.880	0.900
7 Moderate, 8-14	0.875	0.851	0.818	0.845	0.862
8 Severe, 1-3	0.863	0.810	0.771	0.821	0.824
9 Severe, 4-7	0.813	0.772	0.729	0.781	0.789
10 Severe, 8-14	0.751	0.729	0.681	0.734	0.730

ASU1 will be completed on an ePRO device at the clinical study site and at the times detailed in Appendix 1: Schedule of Activities.
 
St. George's Respiratory Questionnaire (SGRQ)
 
The St. George's Respiratory Questionnaire is a well-established instrument, comprising a 50-item questionnaire designed to measure Quality of Life in patients with diseases of airway obstruction, measuring symptoms, impact, and activity.
 
The questions are designed to be self-completed by the participant with a recall over the past 4 weeks [Jones, 1992].
 
Scores are expressed as the percentage of overall impairment with 100 equalling to the worst possible health status and 0 indicating the best possible health status.
 
Scoring in each domain of the SGRQ (Symptoms, Activity, Impacts) and the Total score are described in the St George's Respiratory Questionnaire Manuel (Version 2.3, 2009).
 
SGRQ will be completed on an ePRO device at the clinical study site and at the times detailed in Appendix 1: Schedule of Activities.


Patient Activation Measure (PAM-13)
 
Patient Activation Measure will be used to assess the knowledge, skills and confidence a person has in managing their own health and health care.
 
The PAM contains a series of 13 statements designed to assess the extent of a patient's activation. These statements are about beliefs, confidence in the management of health-related tasks and self-assessed knowledge. Patients are asked to rate the degree to which they agree or disagree with each statement. These answers are combined to provide a single score of between 0 and 100, which represents the patients' concept of themselves as an active manager of their health and health care. There is no specified timeframe on which responses should be based, the questionnaire is suitable to be used to measure changes in activation over time and can be performed before and after an intervention [Hibbard, 2004].
 
The 13 items have four possible response options: (1) disagree strongly, (2) disagree, (3) agree and (4) agree strongly, and an additional "Not applicable" option. The total PAM score is then calculated by dividing the raw score over the number of items answered (not including the non-applicable items) and multiplied by 13. This score is then transformed to a scale with a range of 0-100 based on calibration tables and proprietary PAM algorithm (http://www.insigniahealth.com/). The score will be provided for analysis.

Medication Adherence Report Scale for Asthma (MARS-A)
 
The MARS-A is a 10-item questionnaire where medication use is rated on a 5-point Likert scale (1 indicating 'always' to 5 indicating 'never'). It has been validated as a self-reported measure of adherence with ICS for patients with asthma, and includes generic ("I use it regularly every day") and lung condition-specific questions about medication use ("I only use it when I feel breathless") [Cohen, 2009].
 
The MARS-A 10-Score will be calculated for each participant as the sum of scores for each of the ten questions divided by the number of non-missing responses to the ten questions.
 
If some responses are missing the MARS-A 10-score is calculated as follows for each participant:
 
 
• If eight or more of the questions have been answered, the missing responses for that participant will be imputed to the average score
 



• If less than eight of the questions have been answered, the overall MARS-A 10-score for that participant will be set to missing

---

MARS-A will be completed on an ePRO device at the clinical study site and at the times detailed in Appendix 1: Schedule of Activities.

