#### **9.1.3.5. Medication Adherence Report Scale for Asthma (MARS-A), 10-item questionnaire**

Reported adherence to medication will be assessed with the Medication Adherence Report Scale for Asthma (MARS-A) questionnaire at times shown in the [Schedule of Activities \(SoA\)](#).

The MARS-A is a 10-item questionnaire where medication use is rated on a 5-point Likert scale (1 indicating 'always' to 5 indicating 'never'). It has been validated as a self-reported measure of adherence with ICS for patients with asthma, and includes generic ("I use it regularly every day") and lung condition-specific questions about medication use ("I only use it when I feel breathless") [Cohen, 2009]. The MARS-A has no specified timeframe on which responses should be based but generally refer to the present moment. MARS-A will be completed on an ePRO device at the clinical study site and at the times detailed in the Section 2.

Please refer to the SRM for further details.

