Note: The total PAM score is calculated by dividing the raw score over the number of items answered and multiplied by 13. This score is then transformed to a scale within a range of 0-100 based on calibration tables and proprietary PAM algorithm.

Example : EFF\_T28  
 Protocol : 207040  
 Population : Intent-to-Treat

Page 1 of x

Table 2.xx  
 Summary of Medication Adherence Report Scale - Asthma (MARS-A) Total Score

Visit		Arm 1 (N=xxx)	Arm 2 (N=xxx)	Arm 3 (N=xxx)	Arm 4 (N=xxx)	Arm 5 (N=xxx)
Baseline [1]	n	XX	XX	XX	XX	XX
	Mean	XX.X	XX.X	XX.X	XX.X	XX.X
	SD	X.XX	X.XX	X.XX	X.XX	X.XX
	Median	XX.X	XX.X	XX.X	XX.X	XX.X
	Min.	XX	XX	XX	XX	XX
	Max.	XX	XX	XX	XX	XX
Visit 5 (Month 1)	n	XX	XX	XX	XX	XX
	Mean	XX.X	XX.X	XX.X	XX.X	XX.X
	SD	X.XX	X.XX	X.XX	X.XX	X.XX
	Median	XX.X	XX.X	XX.X	XX.X	XX.X
	Min.	XX	XX	XX	XX	XX
	Max.	XX	XX	XX	XX	XX

[1] Baseline MARS-A 10 total score is taken from screening visit.

Note: MARS-A 10 Total Score is based on the mean score across all ten questions per visit.

*Programming note: repeat for Randomisation visit, Change from Baseline at Visit 5 (Month 1), Visit 10 (Month 6), Change from Baseline at Visit 10 (Month 6), Early Withdrawal*

EFF\_T19

Protocol:207040

Population: Intent-to-Treat

Page 1 of x

Table 2.xx  
Summary of Beliefs in Medicine Questionnaire (BMQ) General Benefit Total Score

Visit		Arm 1 (N=xxx)	Arm 2 (N=xxx)	Arm 3 (N=xxx)	Arm 4 (N=xxx)	Arm 5 (N=xxx)
Baseline [1]	n	xx	xx	xx	xx	xx
	Mean	xx.x	xx.x	xx.x	xx.x	xx.x
	SD	x.xx	x.xx	x.xx	x.xx	x.xx
	Median	xx.x	xx.x	xx.x	xx.x	xx.x
	Min.	xx	xx	xx	xx	xx
	Max.	xx	xx	xx	xx	xx
Visit 5 (Month 1)	n	xx	xx	xx	xx	xx
	Mean	xx.x	xx.x	xx.x	xx.x	xx.x
	SD	x.xx	x.xx	x.xx	x.xx	x.xx
	Median	xx.x	xx.x	xx.x	xx.x	xx.x
	Min.	xx	xx	xx	xx	xx
	Max.	xx	xx	xx	xx	xx

[1] Baseline BMQ total score is taken from screening visit.

Note: BMQ Score is based on the total score across all items within the BMQ measure

Programming note: repeat for Randomisation visit, Change from Baseline at Visit 5 (Month 1), Visit 10 (Month 6), Change from Baseline at Visit 10 (Month 6), Early Withdrawal

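### The SAP scores MARS-A as a plain mean of items keyed in opposite directions, with no reverse-coding step and no stated score direction

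*SAP*

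**What the plan says.** Protocol Section 9.1.3.5 and SAP Section 10.5.3.3 describe the instrument alike: ten items on which "medication use is rated on a 5-point Likert scale", with 1 for always and 5 for never. Both cite the same two items as examples. One concerns regular everyday use (SAP: "includes generic ('I use it regularly every day"). The other concerns use only under symptoms (SAP: "lung condition-specific questions about medication use ('I only use it when I feel breathless").

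The SAP then gives its own item-level formula, the "sum of scores for each of the ten questions divided by the number of non-missing responses to the ten questions", and a missing-item rule: "If eight or more of the questions have been answered, the missing responses for that participant will be imputed to the average score". With fewer than eight answers the score is missing. The footnote to the MARS-A table shell in SAP Appendix 9 repeats the approach: "MARS-A 10 Total Score is based on the mean score across all ten questions per visit".

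None of these places mentions recoding any item or says whether a high score is good or bad. The endpoint is the mean change from screening to Month 6. It is listed as exploratory in Protocol Section 4 and SAP Section 2.2, and SAP Section 7.3.3.4.5 limits it to descriptive statistics.

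**The concern.** On the item about regular daily use, an adherent participant answers always and is coded 1. On the item about use only when breathless, an adherent participant answers never and is coded 5. A plain mean adds the two in the same direction, so they work against each other. A participant who moves towards daily use scores as less adherent on the item that asks about it most directly.

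At stake is whether the trial's self-reported adherence measure has a consistent direction. The trial exists to test whether the connected system improves adherence to a once-daily inhaler, so the mis-signed item is the one closest to what the intervention is meant to change. Readers are also likely to set the MARS-A table beside the sensor results.

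**Working it through.** The plan states no MARS-A figure, so there is none to reproduce. The check applies the written rule to its own coding.

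**Inputs**
- Ten items coded 1 to 5, scored as a plain mean (SAP 10.5.3.3).
- At least one item whose adherent answer is coded 1 and at least one whose adherent answer is coded 5 (the two cited items).
- k, the number of items whose adherent answer is coded 1. This is an assumption: the documents show one such item and do not print the rest. The base case is k = 1, with 2 and 3 shown as a range. The other 10 − k items are taken to have 5 as the adherent answer.
- Higher is read as better. The documents do not say so, but the conflict does not depend on it: whichever direction is chosen, one of the two cited items runs against it.

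**Extremes of the score**
- Fully adherent, as written: [k × 1 + (10 − k) × 5] / 10.
- Fully non-adherent, as written: [k × 5 + (10 − k) × 1] / 10.
- With the k items recoded as 6 − x, the extremes are 5.0 and 1.0.

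**Uniform improvement.** If every item improves by one category, the written score changes by [(10 − k) − k] / 10 = (10 − 2k) / 10. With recoding it changes by 10/10 = +1.0.

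| k | Fully adherent | Fully non-adherent | One-category improvement on all items |
|---|---|---|---|
| 1 | 4.6 | 1.4 | +0.8 |
| 2 | 4.2 | 1.8 | +0.6 |
| 3 | 3.8 | 2.2 | +0.4 |
| Any, recoded | 5.0 | 1.0 | +1.0 |

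**Daily-use item alone.** An improvement of one category changes the written score by −1/10 = −0.1, against +0.1 with recoding. Two categories give −0.2 against +0.2.

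**General form.** Let P be the total improvement, in categories, on the positively worded items and N the total on the others. The written change is (N − P)/10 and the recoded change is (N + P)/10. The error is therefore −2P/10 = −0.2P, and its sign depends only on P. With k = 1 and the nine other items each improving by one category (N = 9):

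| Daily-use item | As written | Recoded | Error |
|---|---|---|---|
| Improves by one (P = 1) | +0.8 | +1.0 | −0.2 |
| Unchanged (P = 0) | +0.9 | +0.9 | 0 |
| Worsens by one (P = −1) | +1.0 | +0.8 | +0.2 |

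**Missing item, k = 1.** A fully adherent participant who answers everything scores (1 + 9 × 5)/10 = 4.6. If that participant skips the daily-use item, the score is 45/9 = 5.0, and filling the gap with the participant's own average leaves it there: (45 + 5)/10 = 5.0. Answering the item at screening and skipping it at Month 6 would show a change of 5.0 − 4.6 = +0.4 with no change in behaviour. With recoding done first, the score is 5.0 either way.

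**The case against.** The strongest objection is that silence is not a rule. The SAP never says that items are left unreversed, and the word score could mean an item score after coding. The data come from an ePRO device whose export format is not described, and Protocol Section 9.1.3.5 ends with "Please refer to the SRM for further details", a manual that is not available here. Recoding upstream is possible. That part stands, and it is why the remedy has to be conditional: recoding data that already arrive recoded would create the error it is meant to remove.

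The objection does not clear the text as written. Where scoring is done elsewhere, SAP Section 10.5.3.3 says so: ACT totals are taken from the ePRO device and not rederived, SGRQ scoring is assigned to its manual, and the PAM score is supplied. For MARS-A it gives a complete formula and a missing-item rule and points to no outside source for the scoring. It also states which end is better for ACT, ASUI and SGRQ, but not for MARS-A. A programmer working from this section would average the responses as coded.

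A reader might infer that every improvement in MARS-A will be understated, and by 20%. The documents do not support that. The error is −0.2P: nil if the positively worded items do not move, and an overstatement if they worsen while the others improve. The 20% figure needs exactly one such item and a uniform improvement, and the documents give neither.

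It is also fair to say that the stakes are low. The endpoint is exploratory, has no test or confidence interval, and is scored identically in all arms. The rule therefore cannot by itself create a difference between arms, although it can shrink or distort one that arises on the daily-use item.

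**Conclusion.** The point holds in a limited form. The derivation in SAP Section 10.5.3.3, followed as written, combines items of opposite direction and fixes no direction for the total. Reading higher as better, improvement in daily use enters with the wrong sign, at −0.1 per category. A one-category improvement on all items would show as +0.8, +0.6 or +0.4 for one, two or three positively worded items, against +1.0. With one such item, the missing-item rule adds a gap of 0.4 between a fully adherent participant who skips the daily-use question and one who answers it.

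These sizes rest on the assumed k, on the remaining items having never as the adherent answer, and on no recoding before the data reach the analysis. A reader might also infer that the sponsor's MARS-A results will be wrong. The documents show only that the written rule would make them so if the responses arrive as coded. Nothing here touches the sensor-based primary endpoint, its power or its type I error.

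**What to change.** In SAP Section 10.5.3.3:

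1. Confirm whether the ePRO export delivers raw or already recoded item responses, and record the answer.
2. If raw, list every positively worded item, including the one on regular daily use, and recode each as 6 − x before averaging and before the missing-item rule is applied. If already recoded, say so and apply no further reversal.
3. State that a higher score means better adherence.
4. Align the footnote of the MARS-A table shell in SAP Appendix 9 with this wording.

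The cost is one query about the export format, a line or two of SAP text and about one line of code. No data collection, sample size or other analysis changes.

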**Beliefs in Medicine Questionnaire (BMQ)**

The BMQ questionnaire consists of the BMQ Specific, which measures perceptions of specific medicines, and the BMQ General, which measures more general beliefs about medicines. All items are scored on a 5-point Likert scale ranging from Strongly Disagree (1) to Strongly Agree (5).

The BMQ Specific questionnaire is formed of the 6 item Necessity and 12 item Concern scales, and the General questionnaire is formed of the 4 item Benefit, 5 item Harm and 3 item Overuse scales.

CCI - This section contained Clinical Outcome Assessment data collection questionnaires or indices, which are protected by third party copyright laws and therefore have been excluded.

Scores obtained for individual items within scales are summed together to provide a total score. The BMQ Specific and General will be completed on an ePRO device at the clinical study site and at the times detailed in Appendix 1: Schedule of Activities.

Biomarkers
PEF and FeNO

 
Participants should not use their rescue medication for at least 6 hours before each FeNO and PEF assessment, unless essential for clinical need. Participants should also withhold ICS/LABA for (1 dosing interval) approximately 12-24 hours prior to FeNO and PEF assessment.
 
PEF and FeNO will be taken in triplicate at the times detailed in Appendix 1: Schedule of Activities. All 3 measures will be recorded in the eCRF.
 
The maximum value from the 3 measures taken at each visit will be used in the calculation of the FeNO and PEF endpoints.
 

Severe Asthma Exacerbations
General

Missing onset or resolution dates will be handled as follows:
 
 
Single event with missing onset and/or resolution dates: 
 
(a) Missing onset date: set onset date = study treatment start date
 
(b) Missing resolution date: set resolution date = study treatment stop date
 
(c) Both missing: imputed per both (a) and (b)
 
 
 
Multiple events, one event with some missing onset/resolution dates; on the assumption any partial date information does not occur during the other events: 
 
(a) Missing onset date: set onset date = max[(resolution date of the nearest previous event) + 1 day, study treatment start date]
 
(b) Missing resolution date: set resolution date = min[(onset date of the nearest subsequent event) - 1 day, study treatment stop date]
 
(c) Both missing: determine the largest gap between study treatment start date and first event onset date, between first event resolution date and next event(s) onset dates (if any), between last event resolution date and study treatment stop date. If there is more than one gap which is the largest, then take the first occurrence. Then impute as follows:  <math display="block">\text{onset date} = (\text{onset date of largest gap}) + 1 \text{ day}</math> <math display="block">\text{resolution date} = (\text{resolution date of largest gap}) + 1 \text{ day}</math> 
 
 
 

#### 10.5.4. Safety

Adverse Events

Adverse events will be coded using the current MedDRA coding dictionary at the time of reporting providing a Preferred Term (PT) and a System Organ Class (SOC) for analysis and reporting.

ADRs and SAEs of Special Interest
ADR and SAE groups of special interest have been defined as SAEs which are included in specified areas of interest for Relvar/Breo. They are identified by groupings of preferred terms based on the Medical Dictionary for Regulatory Activities (MedDRA) dictionary version used in each reporting effort. Groupings or subgroups may be defined, based on relevant combination of preferred terms, or on Standardised MedDRA queries (SMQs).  SAEs of special interest will be confirmed prior to final data, based on the MedDRA version in use at the time

## 10.6. Appendix 6: Reporting Standards for Missing Data

### 10.6.1. Premature Withdrawals

Element	Reporting Detail
General	
 
Participant study completion (as specified in the protocol) is defined as completing all visits of the study including the follow-up phone contact.
 
Withdrawn participants will not be replaced in the study.
 
All available data from participants who are withdrawn from the study will be included in listings and where possible any available data from withdrawn participants will be included in summaries or analyses, unless otherwise specified.
 

### 10.6.2. Handling of Missing Data

Element	Reporting Detail
General	
 
Missing data occurs when any requested data is not provided, leading to blank fields on the collection instrument: 
 
These data will be indicated by the use of a “blank” in participant listing displays. If all data for a specific visit are missing, the visit will be excluded from the display.
 
Answers such as “Not applicable” and “Not evaluable” are not considered to be missing data and will be displayed as such.
 
 
 

MMRM Analysis	
 
All the available assessments taken at scheduled visits will be included in the repeated measures models in which missing data are not explicitly imputed but the correlation between visits for all participants is used to adjust the estimate of treatment effect considering any missing data.
 

Rescue Free Days Endpoint	
 
Handling of missing sensor data is detailed in Section 7.2.2.3 Strategy for Intercurrent (Post-Randomisation) Events, as well Section 10.5.3.2 MDI Device Sensor Assessments.
 

ACT	
 
Handling of missing ACT data is detailed in Section 7.2.3.3 Strategy for Intercurrent (Post-Randomisation) Events.
 

Other PROs	
 
Handling of missing PRO data is detailed in Section 7.3.3.4 Strategy for Intercurrent (Post-Randomisation) Events, as well in Section 10.5.3.3 Patient Reported Outcomes.
 

